6.4. Visit Windows

Data analyzed by-visit-analysis (including efficacy, laboratory data, vital sign and spirometry/PEF) will be summarized by the study scheduled visits described in the study protocol and SAP, "Schedule of Event". The analysis visit windows will be exhaustive so that all available values obtained from unscheduled visits and early termination (ET) visit have the potential to be summarized.

No analysis visit windows will be applied for the study scheduled visits.

CONFIDENTIAL

Page 56 of 86

The following analysis visit windows will be used to map the unscheduled visits and ET visit, based on the study day:

| Visit | Target Day (TD) | Analysis Time Window Based on Study Day ^a |
|---------------------------|--|---|
| Screening 1 | -113 to -17 | -113 to -17 |
| Screening 1a | -57 to -15 | -57 to -15 |
| Baseline | 1 | 1 |
| Visit 3 (Week 2) | 15 | [2, 22] |
| Visit 4 (Week 4) | 29 | [23, 36] |
| Visit 5 (Week 6) | 43 | [37, 50] |
| Visit 6 (Week 8) | 57 | [51, 64] |
| Visit 7 (Week 10) | 71 | [65, 78] |
| Visit 8 (Week 12) | 85 | [79, 92] |
| Visit 9 (Week 14) | 99 | [93, 106] |
| Visit 10 (Week 16) | 113 | [107, 120] |
| Visit 11 (Week 18) | 127 | [121, 134] |
| Visit 12 (Week 20) | 141 | [135, 148] |
| Visit 13 (Week 22) | 155 | [149, 162] |
| Visit 14 (Week 24) | 169 | [163, 176] |
| Visit 15 (Week 26) | 183 | [177, 190] |
| Following visit 15 | a – 15f are optional visits ^b during | up-dosing period |
| Visit 15a (Week 28) | 197 | [191, 204] |
| Visit 15b (Week 30) | 211 | [205, 218] |
| Visit 15c (Week 32) | 225 | [219, 232] |
| Visit 15d (Week 34) | 239 | [233, 246] |
| Visit 15e (Week 36) | 253 | [247, 260] |
| Visit 15f (Week 38) | 267 | [261, 274] |
| Following windows only ap | ply to subjects who entered doubl | e-blind maintenance period |
| Visit 16 (Week 28 to 40) | Target Day (TD) at last visit during up-dosing period ^c + 14 days | [Visit 16 TD ^d - 8 days, Visit 16 TD + 30 days] |
| Visit 17 (V16 + 4 weeks) | Visit 16 TD + 28 days | [Visit 17 TD – 13 days, Visit 17 TD + 14 days] |

| Visit 18 (V16 + 8 weeks) | Visit 16 TD + 56 days | [Visit 18 TD – 13 days, Visit 18 TD + 14 days] |
|---|---|---|
| Visit 19 (V16 + 12 weeks) | Visit 16 TD + 84 days | [Visit 19 TD – 13 days, Visit 19 TD + 14 days] |
| Visit 20 (V16 + 16 weeks) | Visit 16 TD + 112 days | [Visit 20 TD – 13 days, Visit 20 TD + 14 days] |
| Visit 21 (V16 + 20 weeks) | Visit 16 TD + 140 days | [Visit 21 TD – 13 days, Visit 21 TD + 14 days] |
| Visit 22 (Week 52 to 64, V16 + 24 weeks) | Visit 16 TD + 168 days | [Visit 22 TD – 13 days, Visit 22 TD + 14 days] |
| Following window | ws apply to subjects who entered | follow-up period |
| Visit 23 (V16 + 28 weeks) | Target Day (TD) at last visit in pre-dosing/up- dosing/maintenance period ^e + 28 days | [Visit 23 TD – 13 days, Visit 23 TD + 14 days] |
| Visit 24 (V16 + 32 weeks) | Target Day (TD) at last visit in pre-dosing/up- dosing/maintenance period + 56 days | [Visit 24 TD – 13 days, Visit 24 TD + 14 days] |
| Visit 25 (Week 64 to 76, V16 + 36 weeks) | Target Day (TD) at last visit in pre-dosing/up- dosing/maintenance period + 84 days | ≥ Visit 24 TD + 14 days |

^a Study day is calculated relative to the date of first study drug injection.

^b Visit 15a – 15f are optional visits in order to reach 300 mg/day AR101 for at least two weeks. Subjects may reach 300 mg/day AR101 for at least two weeks at any of the optional visits.

^c The last visit during up-dosing period could be any of visit 15, 15a, 15b, 15c, 15d, 15e, or 15f.

^dVisit 16 target day (TD) is defined as target day at last visit during up-dosing period + 14 days.

^e The target day at last visit in pre-dosing/up-dosing/maintenance period could be any of the following visit: 1) visit 15 during up-dosing period; 2) ET visit during up-dosing period; 3) visit 22 during maintenance period; 4) ET visit during maintenance period.

In general, the following order will be used to select the record for analysis at given visit:

- 4. Scheduled visit
- 5. ET or end of study (EOS), whichever comes first if scheduled visit not available
- 6. Unscheduled visit if both scheduled visit and ET/EOT/EOS are not available

For the multiple measurements of the same test in the same window, the following rules will be used to select the analysis value:

- If multiple valid values of a variable within an analysis visit window, the closest from the target study day will be selected.
- If the difference is a tie, the value after the targeted study day will be selected.
- If multiple available values of a variable exist within a same day, then the first value of the day will be selected.

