Subjects who achieve 300 mg/day AR101 for at least 2 weeks during the up-dosing period will be eligible to enter a 24-week maintenance phase in which all subjects will continue to receive AR101 300 mg/day at home. The 24-week maintenance duration will start from when the subject has their day 1 of their post up-dosing DBPCFC at visit 16. (Safety analysis of the maintenance period starts after the second day of the visit 16 post up-dosing DBPCFC.) Subjects will have a monthly clinic visit. If the on-site clinic visit cannot occur, phone visits can take place as long as there are no changes to the subject's AR101 dose. Subjects in the dupilumab treatment group will be randomly assigned to either continue dupilumab at the same dose as administered during the up-dosing

period or to receive placebo. Subjects who received placebo during the up-dosing phase will continue to receive placebo in the maintenance phase. After 24 weeks of AR101 and 24 weeks of dupilumab or placebo, subjects will undergo a post maintenance DBPCFC to assess the level of peanut sensitivity at the end of the maintenance period.

Subjects who do not achieve 300 mg/day AR101 for at least 2 weeks at visit 16 and are not permitted to enter the maintenance phase, will enter a 12-week follow-up period (see below). The procedure for monitoring subjects for safety after in-clinic dosing is the same as for the up-dosing visits except that the initial period required for post-dose observation may be shortened to 30 minutes.

Double-Blind, Placebo-Controlled Food Challenge

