 - a. During the COVID-19 pandemic, measurements of FeNO no longer need to be completed while on study (at the discretion of the investigator). Additionally, if spirometry cannot be completed after enrollment, peak flow may be performed instead at the discretion of the investigator (although spirometry is still required at screening).
- 10. Only for subjects who discontinue for GI AEs. If applicable, after week 64 PEESS will be collected by phone.
- 11. On the day of the DBPCFCs, blood draws for optional exploratory research-will be performed before the DBPCFC is performed.
- 12. Clinic visits are monthly. However, SC study drug administration is Q2W and dosing diaries for AR101 and allergic symptoms are done daily.
- 13. The time points listed in this table correspond with the bi-weekly up-dosing schedule (Table 2). These time points may no longer be accurate following adjustments to the planned up-dosing period. As of Amendment 3, the up-dosing period has been permitted to be extended to accommodate dose reductions and re-escalation as well as COVID-19 restrictions of in-clinic visits. This extension permits a maximum up-dosing period of 40 weeks, while 28 weeks is ideal (consisting of 4 weeks pretreatment, 22 to 34 weeks of up-dosing, and at least 2 weeks at the maximum dose).
- 14. If subjects are not able to go into the clinic for the DBPCFC within the target time frame, the DBPCFC can be started up to 7 days before and 30 days after the target date for visit 16, 22, and/or 25.
- 15. Study drug administration at unscheduled and/or optional visits 15a-f is to be documented in the unscheduled visits folder.

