11.5. Additional Statistical Data Handling Conventions

The following analysis and data conventions will be followed:

Definition of baseline:

• The baseline assessment will be the latest, valid pre-first-dose assessment available.

General rules for handling missing data:

• Rules for handling missing data for assessment (other than efficacy)

CONFIDENTIAL

Page 100 of 118

- If the start date of an AE or concomitant medication is incomplete or missing, it will be assumed to have occurred on or after the intake of study medication, except if an incomplete date (eg, month and year) clearly indicates that the event started prior to treatment. If the partial date indicates the same month or year of the intake of study medication date, then the start date by the study medication intake date will be imputed; otherwise, the missing day or month by the first day or the first month will be imputed.
- No imputations for missing laboratory data, vital sign data, or physical examination data will be made.

Visit windows:

• Assessments taken outside of protocol allowable windows will be displayed according to the case report form (CRF) assessment recorded by the investigator.

Unscheduled assessments:

• Extra assessments (laboratory data or vital signs associated with nonprotocol clinical visits or obtained in the course of investigating or managing AEs) will be included in listings, but not summaries. If more than 1 laboratory value is available for a given visit, the first observation will be used in summaries, and all observations will be presented in listings.

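### SAP 6.4 times the maintenance windows from the visit 16 target day, not the actual visit 16, and leaves overlapping windows unresolved, so some early-termination and unscheduled values can be mapped ambiguously or to the next visit (minor)

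*SAP*

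**What the plan says.** **Protocol.** Section 6.1 fixes the maintenance clock on an actual date: "The 24-week maintenance duration will start from when the subject has their day 1 of their post up-dosing DBPCFC at visit 16". Section 8.5 repeats this, and Table 4 schedules later visits as visit 16 plus a number of weeks. Footnote 14 to Table 4 allows the challenge date to move: "the DBPCFC can be started up to 7 days before and 30 days after the target date for visit 16, 22, and/or 25".

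**SAP 6.4.** The windows have a limited job: "The following analysis visit windows will be used to map the unscheduled visits and ET visit, based on the study day". For the rest, "No analysis visit windows will be applied for the study scheduled visits".

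- Footnote d defines the visit 16 "target day (TD) is defined as target day at last visit during up-dosing period + 14 days".
- The visit 16 window is "Visit 16 TD ^d - 8 days, Visit 16 TD + 30 days".
- The visit 17 target is "Visit 16 TD + 28 days", with a window from 13 days before to 14 days after it. Visits 18 to 22 follow the same pattern at 28-day steps.
- Footnote e anchors visits 23 to 25 on the last treatment-period visit: visit 15, an ET visit in up-dosing, visit 22, or an ET visit in maintenance.
- A scheduled record outranks an ET or end-of-study record, which outranks an unscheduled one. The tie-break rules choose among several values in one window.

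**Protocol 11.5.** Extra laboratory and vital sign values "will be included in listings, but not summaries". SAP 6.4 makes values from unscheduled visits eligible for summaries. SAP 1.2.3 does not list this among its changes from the protocol.

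**The concern.** The two documents run different clocks. The protocol counts maintenance from the day the visit 16 challenge starts; the SAP counts from a nominal day that takes no account of when it started. If visit 16 is late enough, an ET value is labelled with a later visit than the time on maintenance supports.

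The ET visit collects peanut-specific IgE, laboratory tests, vital signs and spirometry (Protocol Table 4). A subject who terminates in maintenance has no scheduled visit 22, so the ET record can fill that slot. Percent change in peanut-specific IgE to visit 22 is a secondary endpoint whose main analysis imputes missing values (SAP 5.6.2 and 10.1). A mis-timed ET value would enter that analysis as an observed 24-week value when it should be missing and imputed.

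Separately, a value that lies in two windows has no defined visit, so two programmers could follow the SAP and produce different by-visit tables.

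**Working it through.** **Inputs.** Target days of visit 15 (day 183) and visit 15f (day 267), and the window limits, from SAP 6.4. Allowed shift of visit 16 from target, -7 to +30 days, from Protocol Table 4 footnote 14. Windows are counted inclusively.

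**Reproducing the plan's own days.** From visit 15: 183 + 14 = 197 (week 28); 197 + 168 = 365 (week 52); 365 + 84 = 449 (week 64). SAP 10.6 gives D365 for visit 22 and D449 for visit 25, so the target-day chain reproduces. From visit 15f: 267 + 14 = 281 (week 40), 449 (week 64) and 533 (week 76), which match the stated upper ends.

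**Effect of the anchor.** Let actual visit 16 fall on A = TD + s. A value exactly 28k days later falls on TD + s + 28k. The SAP window for visit 16 + k runs from TD + 28k - 13 to TD + 28k + 14. The value lies in its own window only if -13 ≤ s ≤ 14.

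- Allowed shifts: -7 to +30, which is 38 values.
- Mapped correctly: -7 to +14, which is 22 of 38.
- Past its own window: +15 to +30, which is 16 of 38.

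These are counts of permitted shifts, not frequencies of subjects.

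**Worked example.** Last up-dosing visit is visit 15, so TD = 197. Visit 16 is on day 227 (s = 30).

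| Visit | Day on the protocol clock | SAP window | Where that day falls |
|---|---|---|---|
| 17 | 255 | 212-239 | visit 18 |
| 18 | 283 | 240-267 | visit 19 |
| 19 | 311 | 268-295 | visit 20 |
| 20 | 339 | 296-323 | visit 21 |
| 21 | 367 | 324-351 | visit 22 |
| 22 | 395 | 352-379 | past visit 22 |

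The visit 22 window is 352 - 227 = 125 to 379 - 227 = 152 days after the actual visit 16, or about 18 to 22 weeks, although it is labelled week 24. An ET visit at 20 weeks (227 + 140 = day 367) is taken as the visit 22 value.

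A maintenance ET from day 380 to 394 is still short of 24 weeks but past the visit 22 window. If footnote e anchors visit 23 on the ET date itself, visit 23 opens at ET + 28 - 13 = ET + 15, so that ET value has no window, although SAP 6.4 intends its windows to leave nothing out.

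**Overlaps** (smaller upper limit minus larger lower limit, plus 1).

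- Visits 16 and 17: TD - 8 to TD + 30 against TD + 15 to TD + 42, so 30 - 15 + 1 = 16 days (212 to 227 in the example). All 16 are nearer the visit 17 target (0 to 13 days) than the visit 16 target (15 to 30 days).
- Visits 15 and 16: 190 - 189 + 1 = 2 days. With visit 15f last: 274 - 273 + 1 = 2 days.
- Visits 24 and 25: visit 24 ends, and visit 25 begins, on visit 24 TD + 14, so 1 day.

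The tie-break rules do not cover one value in two windows.

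**After re-anchoring on A.** Visit 17 is A + 15 to A + 42, visit 18 is A + 43 to A + 70, and so on to visit 22 at A + 155 to A + 182. With visit 16 closed at A + 14 these rows meet with no overlap, and a value at A + 28 maps to visit 17 for all 38 shifts.

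**The case against.** Most of the data never meet these windows. Scheduled visits are not windowed and take priority. No food challenge is scheduled at the ET visit, so the primary and first secondary endpoints are out of reach. SAP 5.6.3 sets no formal hypothesis for maintenance. All of this stands.

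The visit 16/17 overlap also does little. The visit 16 row applies only to subjects who entered maintenance, and their scheduled visit 16 record is used first. Visit 17 has no scheduled IgE, laboratory tests or spirometry. What is left is mainly vital signs, weight and the EASI and ACQ scores when a scheduled value is missing. This also stands, and in the overlap the assignment is undefined rather than wrong.

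A reader might infer that on-treatment ET values from the end of maintenance are filed under off-treatment follow-up. The documents do not support that:

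- Footnote e does not tie follow-up directly to the visit 16 target. For a subject who terminates in maintenance the anchor is the ET visit. An ET on day 395 gives a visit 23 target of 423 and a window opening on day 410, so the ET value cannot fall in it.
- Completers do inherit the visit 16 target through visit 22 (365 + 28 = 393, window 380 to 407), but their visit 22 is scheduled and is not windowed. Only an unscheduled value could land there, and a scheduled visit 23 value outranks it.
- SAP 3.3 defines the safety periods by actual challenge and ET dates, so SAP 6.4 moves no on-treatment time into follow-up.

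The objection does not remove the anchor error for visits 17 to 22, the ET value at 20 weeks read as visit 22, or the missing rule for a value in two windows.

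**Conclusion.** Wrong as written, with limited reach; minor.

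- **Anchor.** The windows for visits 17 to 22 disagree with the protocol's maintenance clock. For values taken at exact 4-week multiples, the mapping fails when visit 16 is 15 to 30 days late.
- **Overlaps.** 16 days (visits 16/17), 2 days (visits 15/16) and 1 day (visits 24/25), all without a rule.
- **Reach.** The visit 22 peanut-specific IgE secondary endpoint, and by-visit laboratory, vital sign and spirometry summaries, through ET and unscheduled values only. For IgE the effect is mainly on the multiple-imputation analysis; the LOCF sensitivity analysis could carry an ET value forward in any case.
- **Size.** Not known. It depends on how many subjects had visit 16 at least 15 days late and then terminated in maintenance or missed a scheduled value. The documents give neither count.

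The reading of a maintenance ET with no window assumes that footnote e means the ET date itself, since an ET visit has no target day of its own. The conflict with Protocol 11.5 concerns unscheduled values; I read that section as not covering the ET visit, which is in the protocol's own schedule.

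**What to change.** In the SAP 6.4 table, before database lock:

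1. Anchor visits 17 to 22 on A, the actual date of day 1 of the visit 16 challenge: visit 17 = A + 15 to A + 42, continuing in 28-day steps to visit 22 = A + 155 to A + 182.
2. Start the visit 16 window on the day after the last up-dosing visit's window ends (day 191 when visit 15 is last, day 275 when visit 15f is last) and close it at A + 14. Moving only the lower limit to TD - 7 is not enough: 197 - 7 = 190, which visit 15 still holds.
3. Anchor visits 23 to 25 only on L, the actual date of the last treatment-period visit, and start visit 25 at visit 24 TD + 15 (L + 56 + 15 = L + 71).
4. End each subject's maintenance rows at L + 14, where follow-up takes over. Otherwise an ET at A + 140 gives a visit 23 window of A + 155 to A + 182, which is also the visit 22 row. When visit 22 itself is late, extend its row to L + 14.
5. Reconcile SAP 6.4 with Protocol 11.5 on whether unscheduled laboratory and vital sign values may enter summaries, and record any departure in SAP 1.2.3.

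The cost is one table, its footnotes and the derivation program. No new data are needed.

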7. INTERIM ANALYSIS

No interim analysis is planned.

An unblinded primary analysis will be performed once all subjects in the study have completed the 28 to 40-week treatment period (visit 16 or earlier for those subjects who are withdrawn prematurely from the study). If performed, the primary analysis will be considered the final analysis for the primary endpoint and secondary efficacy endpoints up to visit 16.

10. APPENDIX

10.1. Summary of Statistical Analyses

Efficacy Analysis:

| Endpoints | Analysis Population | Primary Statistical Method | Supportive/Sensitivity Statistical Method | Subgroup Analysis | Other Analyses |
|---|------------------------|---|---|----------------------|----------------------|
| Primary Endpoint | | | · | | · |
| Proportion of subjects treated with dupilumab plus AR101 vs placebo plus AR101 who "pass" a post up- dosing DBPCFC with 2044 mg (cumulative) peanut protein at visit 16 | mFAS, FAS | Cochran-Mantel-Haenszel test/ MI for missing due to COVID-19, otherwise missing data as non-responder | Cochran-Mantel- Haenszel test with available visit 16 DBPCFC data | Yes | Bar chart |
| Secondary Endpoint | | | | | |
| Change in cumulative tolerated dose (log transformed) of peanut protein during a DBPCFC from baseline to visit 16 | mFAS, FAS | ANCOVA model/ MI for missing due to COVID-19, otherwise missing data imputed by BOCF method | ANCOVA model with available visit 16 DBPCFC data; MI method; van Elteren test with LOCF method/with available visit 16 DBPCFC data for change in cumulative tolerated dose | Yes | Bar chart |
| Proportion of subjects treated with dupilumab plus AR101 vs placebo plus AR101 who reach 300 mg/day dose of AR101 by visit 16 | mFAS, FAS | Cochran-Mantel-Haenszel test | No | Yes | Bar chart |
| Time from randomization to the first- time subjects reach the 300 mg/day dose of AR101 during up-dosing treatment phase (up to visit 16) | mFAS, FAS | Kaplan-Meier estimates; Cox regression model | No | No | Kaplan-Meier plot |

CONFIDENTIAL

Page 63 of 86

| Endpoints | Analysis Population | Primary Statistical Method | Supportive/Sensitivity Statistical Method | Subgroup Analysis | Other Analyses |
|---|------------------------|---|--|----------------------|-------------------|
| Proportion of subjects (continuously) treated with dupilumab plus AR101 vs placebo plus AR101 who 'pass' a DBPCFC with 2044 mg (cumulative) peanut protein at visit 22 | FAS- maintenance | Cochran-Mantel-Haenszel test/ MI for missing due to COVID-19, otherwise missing data as non-responder | Cochran-Mantel- Haenszel test with available visit 22 DBPCFC data | Yes | Bar chart |
| Change in the cumulative tolerated dose (log transformed) of peanut protein during a DBPCFC from baseline to visit 22 in subjects (continuously) treated with dupilumab plus AR101 vs placebo plus AR101 | FAS- maintenance | ANCOVA model/ MI for missing due to COVID-19, otherwise missing data imputed by BOCF method | ANCOVA model with available visit 22 DBPCFC data; MI method; van Elteren test with LOCF method/with available visit 22 DBPCFC data | Yes | Line plot |
| Proportion of subjects (previously) treated with dupilumab plus AR101 vs placebo plus AR101 who 'pass' a DBPCFC with 2044 mg (cumulative) peanut protein at visit 22 | FAS- maintenance | Cochran-Mantel-Haenszel test/ MI for missing due to COVID-19, otherwise missing data as non-responder | Cochran-Mantel- Haenszel test with available visit 22 DBPCFC data | Yes | Bar chart |
| Change in the cumulative tolerated dose (log transformed) of peanut protein during a DBPCFC from baseline to visit 22 in subjects (previously) treated with dupilumab plus AR101 vs placebo plus AR101 | FAS- maintenance | ANCOVA model/ MI for missing due to COVID-19, otherwise missing data imputed by BOCF method | ANCOVA model with available visit 22 DBPCFC data; MI method; van Elteren test with LOCF method/with available visit 22 DBPCFC data | Yes | Line plot |
| Percent change from baseline to visit 16 in peanut-specific IgE in subjects treated with dupilumab plus AR101 vs subjects treated with placebo plus AR101 | mFAS, FAS | Rank-based ANCOVA model, missing data imputed by MI method | ANCOVA model with LOCF method | No | Line plot |
| Percent change from baseline to visit 22 in peanut-specific IgE in subjects (continuously) treated with dupilumab plus AR101 vs subjects treated with placebo plus AR101 | FAS- maintenance | Rank-based ANCOVA model, missing data imputed by MI method | ANCOVA model with LOCF method | No | Line plot |

| Endpoints | Analysis Population | Primary Statistical Method | Supportive/Sensitivity Statistical Method | Subgroup Analysis | Other Analyses |
|--|------------------------|--|--|----------------------|-------------------|
| Percent change from baseline to visit 25 in peanut-specific IgE in subjects (continuously) treated with dupilumab plus AR101 vs subjects treated with placebo plus AR101 | FAS- maintenance | Rank-based ANCOVA model, missing data imputed by MI method | ANCOVA model with LOCF method | No | Line plot |

Safety Analyses:

| Endpoint | Analysis Populations | Statistical Method | Supportive Analysis | Subgroup Analysis | Other Analyses |
|---|----------------------|------------------------|---------------------|------------------------------|----------------|
| Adverse events | SAF, SAF-maintenance | Descriptive statistics | No | Yes, for selected AE summary | No |
| Laboratory measures | SAF, SAF-maintenance | Descriptive statistics | No | No | No |
| Vital sign | SAF, SAF-maintenance | Descriptive statistics | No | No | No |
| Spirometry | SAF, SAF-maintenance | Descriptive statistics | No | No | No |
| Daily allergy symptom diary during up-dosing period | mFAS, FAS | Descriptive statistics | No | No | No |

